Statistical Methodology	
One goal of the analysis is to demonstrate safety, which does not require statistical significance.
 
The other primary goal of the analysis is to assess efficacy of hAF by reducing inflammation in COVID-19 patients, potentially leading to improved clinical outcomes. This will be assessed by measurement of C-reactive protein levels before and after the intervention.
 
Secondary outcomes include:
 

1. Death within 30 days

2. ICU-free days at 30 days

3. Hospital length of stay

4. Need for invasive mechanical ventilation

5. Biomarker levels (interleukin-6, d-dimer, lactate dehydrogenase)

6. Need for ECMO

7. Major adverse cardiac events

8. Patient-reported functional status

\*Enrolled subjects will need to meet blood pressure requirements prior to IP administration, detailed below

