## 3. ENDPOINTS

### Primary Endpoint:

- C-reactive protein (CRP) levels measured before and after treatment
- Whether the patient experienced any post-randomization, study-related Adverse Events (AEs) while on study (up to 5 days) of treatment.

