## 6. STUDY DESIGN AND PROCEDURES

1. Patients will be screened via the electronic medical system, and/or noted and communicated to the study team by physicians in the units.
2. Patient will be called for e-consent.
3. Patients of childbearing potential will receive a pregnancy test
4. Enrolled patients will be randomized to intervention or control with random permuted blocks of 2-4 via sealed envelope or secured electronic randomization tool that will be selected after consent. Patients or treating clinicians will not be notified of treatment assignment.
5. Amniotic fluid will be procured by the Cell Therapy and Regenerative Medicine group here at the University of Utah. Product will be delivered, either frozen or thawed, by this group to the relevant hospital unit/floor.
6. After consent, but prior to initial intervention, the following measurements will be collected:
  - a. Demographics (age, sex, height, weight, race/ethnicity, study hospital admit date and time)
  - b. Medical history
  - c. Concomitant medications
  - d. Confirmation of negative pregnancy test, if applicable
  - e. Date of symptom onset
  - f. Date of confirmed SARS-CoV-2 positivity by RT-PCR
  - g. Vital signs (heart rate, blood pressure, oxygen saturation, respiratory rate, temperature)
    - a) Patients must have a blood pressure of <160/96 mmHg prior to receiving study IP
    - b) Patients must have a pulse of <110 beats per minute prior to receiving study IP
  - h. Glasgow Coma Scale
    - a) Patient must have a GCS score of  $\geq 14$  prior to consent
  - i. Respiratory support modality and settings
  - j. Complete blood count with auto differential
  - k. Complete metabolic panel
  - l. Blood glucose (for patients with diabetes)
  - m. Inflammatory biomarkers (interleukin-6, c-reactive protein, d-dimer, lactate dehydrogenase)
  - n. Results of chest x-ray and/or chest CT, if available.
7. Patients will receive either 10ml IV hAF or 10ml normal saline (control) each day for 5 consecutive days. hAF and saline with similar lot numbers will be prepared in order to maintain blinding between both clinicians and patients.
8. For 3 hours following IP administration, patients will be placed on continuous monitoring (e.g., pulse oximetry, blood pressure) and monitored for infusion reactions.
9. Assessments on Days 1-5 will include:
  - a. Intervention or control date and time

- b. Vital signs (heart rate, blood pressure, oxygen saturation, respiratory rate, temperature)

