  - a) Patient must have a blood pressure of <160/96 mmHg prior to receiving study IP
  - b) Patient must have a pulse of <110 beats per minute prior to receiving study IP
    - i. In the event that a patient does not meet blood pressure and/or pulse criteria for IP administration, these vital signs will be rechecked every hour until they have returned to the necessary range.
- c. Glasgow Coma Scale
- d. Respiratory support modality and settings
- e. Blood glucose (for patients with diabetes)
- f. Results of chest x-ray and/or chest CT, if available.
- g. Concomitant medications

10. Day 6 (post-intervention) assessment will include:

- a. Vital signs (heart rate, blood pressure, oxygen saturation, respiratory rate, temperature)
- b. Glasgow Coma Scale
- c. Respiratory support modality and settings
- d. Complete blood count with auto differential\*
- e. Complete metabolic panel\*
- f. Blood glucose (for patients with diabetes)
- g. Inflammatory biomarkers (interleukin-6, c-reactive protein, d-dimer, lactate dehydrogenase)\*
- h. Results of chest x-ray and/or chest CT, if available
- i. Concomitant medications

\*Patients who have been discharged from the hospital prior to Day 6 will be asked to return to the hospital or an outpatient clinic for Day 6 lab work.

11. At ICU discharge (if applicable) and hospital discharge, the following will be gathered:

- a. Intervention or control date and time
- b. Vital signs (heart rate, blood pressure, oxygen saturation, respiratory rate, temperature)
- c. Glasgow Coma Scale
- d. Respiratory support modality and settings
- e. Blood glucose (for patients with diabetes)
- f. Results of chest x-ray and/or chest CT, if available.

12. The following data will be collected following hospital discharge:

- a. Last available results of chest x-ray(s) and/or chest CT(s), if available.
- b. ICU admit and discharge dates and times (if applicable)
- c. Hospital floor admit and discharge dates and times
- d. Dates and times of intubation and extubation (if applicable)
- e. Tracheostomy (if applicable)
- f. ECMO status (and settings, if applicable)
- g. Major adverse cardiac events

- h. Discharge date and time
- i. Discharge location
- j. Concomitant medications
  - a) Including but not limited to current COVID-19 therapies not approved by the FDA, and non-pharmaceutical therapies
- k. Date and time of death (if applicable)

13. Safety assessments will be performed at 30, 60, 90 and 180 days (+/- 7 days) post-discharge

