- a. Safety assessments will include a defined script inquiring about any new or remaining symptoms (e.g., shortness of breath), sleep quality, if the patient feels they are back to baseline and if they have any positive or negative feedback regarding the IP. Open-ended questions regarding any additional concerns the participant may have as well as a specific question regarding any health events or hospitalizations since the last assessment will also be asked.
- b. These assessments will be performed remotely via telephone by study staff. If the assessment is positive (i.e., if the patient reports AEs that are determined to be related to study drug), a clinician will arrange a telemedicine visit to follow up.

14. At 1, 3, 6, and 12 months post-discharge, patients will be emailed a REDCap survey link in order to complete several surveys: PROMIS measures including Dyspnea Severity, Physical Function, Sleep Disturbance, Anxiety, and Depression, as well as the PTSD Checklist (PCL).

- a. If the patient is still hospitalized at any of these time points, respiratory settings and details of physical therapy progress will be gathered from the chart instead.
- b. Window: 1 month +/- 7 days, 3/6/12 months +/- 14 days

15. If a patient is discharged prior to receiving the 5-days of IP administration the patient will still be followed for the duration of the study

Primary Outcome:

1. C-reactive protein levels as assessed prior to and following intervention.

Secondary Outcomes:

1. Death within 30 days
2. ICU-free days at 30 days
3. Hospital length of stay
4. Need for invasive mechanical ventilation
5. Biomarker levels (interleukin-6, d-dimer, lactate dehydrogenase)
6. Need for ECMO
7. Major adverse cardiac events
8. Patient-reported functional status

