## **8. STATISTICAL CONSIDERATIONS**

### **Statistical Methods**

This is a trial with patients randomized to two groups: (1) treatment group with hAF administered intravenously (n=30), (2) control group with intravenous administration of a saline control (n=30). Both groups will receive standard of care in addition to these treatments.

Descriptive statistics, including mean (SD) and median (interquartile range), will be used to assess patient characteristics, and clinical and biomarker outcomes. Comparisons will be made stratified on ICU vs floor status at enrollment for variables. Categorical characteristics will be compared using chi-square test or Fisher exact test. Continuous characteristics will be compared using independent samples t-test or Wilcoxon-Mann-Whitney test. 95% Confidence intervals and *p*-values will be reported from all comparisons. Statistical analyses will be conducted in R and STATA, significance will be assessed at the 0.05 level and all tests will be two-tailed.

Safety will be assessed by descriptive reporting of the incidence proportion of study-related safety adverse events in each study group, with one-sided 95%

binomial exact confidence intervals. No statistical hypothesis test is planned to assess safety, which is consistent even with large Phase III trials. The table below displays the number of patients, out of 30, experiencing no adverse event and the corresponding lower-bound of the 95% exact confidence interval.

Number of Patients with no Related Adverse Events	Number of Patients Experiencing a Related Adverse Event	Lower-bound of the 95% Exact Binomial Confidence Interval for Safety
30	0	90%
29	1	85%
28	2	80%
27	3	76%

If there are 30 patients in the hAF group and if all patients in the hAF group complete the study without experiencing an adverse event we will be able to state with 95% confidence that the safety of hAF is at least 90%.

Exploratory outcomes for safety include, but are not limited to, the following:

- Whether the patient experienced any post-randomization AEs while on study (regardless of relatedness to study participation)
- Whether the patient experienced any post-randomization serious AEs while on study
- Whether the patient experienced any post-randomization unexpected AEs while on study.

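### The plan does not name the CRP contrast for the primary efficacy comparison, and the only tests it names ignore baseline CRP; a pre-specified log-CRP ANCOVA would usually gain precision at almost no cost

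*Combined protocol and SAP*

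**What the plan says.** Three places define the efficacy variable, and none gives a contrast:

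- Synopsis, Statistical Methodology: "This will be assessed by measurement of C-reactive protein levels before and after the intervention".
- Section 3, Primary Endpoint: "C-reactive protein (CRP) levels measured before and after treatment".
- Section 6, Primary Outcome: "C-reactive protein levels as assessed prior to and following intervention". This is the only primary outcome listed there.

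The measurement times are clear. Section 6, item 6m lists "Inflammatory biomarkers (interleukin-6, c-reactive protein, d-dimer, lactate dehydrogenase") before the first dose. Item 10, which begins "Day 6 (post-intervention) assessment will include", lists the same panel, and patients discharged early are asked to come back for it.

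Section 8, Statistical Methods, does not mention CRP. Its descriptive statistics "will be used to assess patient characteristics, and clinical and biomarker outcomes". It then states "Comparisons will be made stratified on ICU vs floor status at enrollment for variables" and "Continuous characteristics will be compared using independent samples t-test or Wilcoxon-Mann-Whitney test". Testing is two-sided at 0.05. No transformation, baseline covariate or rule for choosing between the two tests is given. The Sample Size Justification sets 30 per group without an SD, an effect or a power for CRP.

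**The concern.** Two things are left open. The first is which CRP quantity is compared between arms. The second is whether the pre-dose CRP, which is collected anyway, is used to reduce the variance of that comparison. On the plan's wording it is not used as a covariate.

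The sample size is fixed without reference to CRP, so any extra precision must come from the analysis. Among the unadjusted tests, the better choice depends on the correlation between baseline and Day 6. The Day 6 value does better when the correlation is low, and the change does better when it is high. The text available does not give that correlation, so an unadjusted choice made now could be the weaker one. Adjusting for baseline largely removes the need to guess.

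**Working it through.** **The plan's own figure.** The 30 per group cannot be reproduced for CRP, because no SD, power or between-arm effect is stated.

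**Inputs from the plan.** 30 per arm and two-sided 0.05 (Section 8). Section 2 hypothesises a 50% fall in mean CRP, worded within the hAF arm. I take it as a between-arm ratio of 0.5, a log difference of ln 2 = 0.693.

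**Assumed inputs.** Log-normal CRP; log-SD (s) 1.0 at both times, range 0.8 to 1.2; correlation r of 0.3, 0.5 and 0.7, with lower values examined below.

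**Standard errors of the log ratio, n = 30 per arm.**

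- Log Day 6 t-test: s × √(2/n) = √(2/30) = 0.258.
- Log change t-test: s × √(2(1 − r)) × √(2/n).
- ANCOVA: s × √((1 − r²)(1 + 1/(2n − 4))) × √(2/n). The factor 1 + 1/56 pays for estimating the slope.

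Example at r = 0.5: ANCOVA SE = √(0.75 × 57/56) × 0.258 = 0.226.

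Power is from the noncentral t distribution with noncentrality 0.693/SE, on 58 df (57 for ANCOVA).

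| r | SE: ANCOVA / Day 6 / change | Power: ANCOVA | Power: better log t-test |
|---|---|---|---|
| 0 | 0.260 / 0.258 / 0.365 | 74.4% | 75.2% |
| 0.3 | 0.248 / 0.258 / 0.306 | 78.3% | 75.2% |
| 0.5 | 0.226 / 0.258 / 0.258 | 85.6% | 75.2% |
| 0.7 | 0.186 / 0.258 / 0.200 | 95.6% | 92.6% |

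Over log-SD 0.8 to 1.2 and r from 0.3 to 0.7, the gain runs from 0.6 points (log-SD 0.8, r = 0.7, where both exceed 98%) to 11.6 points (log-SD 1.2, r = 0.5: 71.1% against 59.5%).

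**The open contrast.** By simulation at r = 0.5, with log-SD 1.0 and placebo CRP also assumed to halve by Day 6, the untransformed readings that the wording allows range from about 15% power (t-test on absolute change) to about 73% (Wilcoxon on the Day 6 value). The low end depends on the assumed placebo course: it is about 37% if placebo CRP does not change.

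**Where the gain stops.**

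1. *Low correlation.* ANCOVA and Day 6 variances are equal when (1 − r²) × 57/56 = 1, so r = √(1/57) = 0.13. Allowing for the lost degree of freedom gives 0.135. At r = 0 the interval is 0.9% wider. With an uninformative ICU/floor term as well, compared with an unstratified test, break-even is 0.19 and the interval at r = 0 is 1.9% wider.
2. *Slope near 1.* Let Day 6 log-SD be k times baseline log-SD. The change has variance 1 + k² − 2rk, and ANCOVA has k²(1 − r²) × 57/56. At r = 0.7, k = 1.3 (slope 0.91): 0.870 against 0.877, ratio 1.008, power 80.8% against 80.4%. At r = 0.8, k = 1.25 (slope 1): 0.5625 against 0.5725, ratio 1.018, power 94.1% against 93.7%.
3. *Moderately heavy tails.* With log-CRP errors from an unscaled bivariate t with 5 df (SD √(5/3) = 1.29), power at r = 0.3, 0.5 and 0.7 is 59.4, 67.4 and 82.2% for log ANCOVA. The better unadjusted Wilcoxon has 61.7, 62.0 and 82.5%. They are roughly level at 0.3 and 0.7.
4. *Very heavy tails.* With unscaled t errors on 3 df (SD √3 = 1.73), log ANCOVA has 43–44, 49–50 and 64–67%, the better unadjusted Wilcoxon 51–54, 48–54 and 71–75%, and rank ANCOVA 55–58, 59–63 and 71–78%. These levels must not be compared with the table, because the SD differs; with SD held at 1.0, log ANCOVA has about 84, 90 and 96%. The ordering is the result: log ANCOVA is generally behind Wilcoxon, and rank ANCOVA does as well as or better than both.

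Under log-normal data rank ANCOVA has 76, 83 and 93%, so it costs little as a sensitivity analysis. Type I error of both ANCOVAs was 4.5 to 5.3%, including under t with 3 df.

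**The case against.** The strongest reply is that the named tests are valid, that ICU/floor stratification is already planned, and that baseline adjustment is an efficiency preference whose size rests on an SD and a correlation that the text available does not give. Part of Section 4's pilot account was not available to this review and may hold CRP data. This stands as a limit on the size of the gain. It does not reverse the direction over the range examined, outside the limits listed in the working.

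A second reply is that the sentence on tests speaks of characteristics and so may concern baseline variables only. But the same paragraph opens with biomarker outcomes and names no other test for continuous data. On the narrower reading the primary efficacy endpoint would have no named between-arm test at all.

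Three stronger inferences are tempting, and the documents do not support them:

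- *That the planned comparison is biased.* It is not: unadjusted tests are valid under randomisation.
- *That the open wording means the most favourable result will be picked after unblinding.* Nothing in the plan suggests this, and naming any single variable and test in advance removes the possibility.
- *That ANCOVA always wins.* It does not, as the four limits show.

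**Conclusion.** The concern holds as a cheap improvement, not as the correction of an error. The CRP contrast is not stated in the text available, and the named tests leave out a baseline value that the trial already collects. Under log-normal CRP with equal log-SDs, log ANCOVA gains 0.6 to 11.6 percentage points of power over the better log t-test for correlations of 0.3 to 0.7 and log-SDs of 0.8 to 1.2.

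That size rests on assumed values and on reading the 50% hypothesis as a between-arm ratio. Where the gain fails with roughly normal log-CRP, the loss is small. Heavy tails are the material exception, and a rank-based sensitivity analysis covers it.

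**What to change.** In Section 8, before unblinding, name one primary efficacy analysis: ANCOVA of log Day 6 CRP on arm, with log baseline CRP and ICU/floor status as covariates. Report the hAF/placebo ratio of geometric means with a two-sided 95% confidence interval and p-value, and say how values below the assay limit are logged. Name rank ANCOVA on baseline CRP as the sensitivity analysis. In Section 2, restate the hypothesis as a between-arm ratio.

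The cost is an interval about 1 to 2% wider if baseline CRP proves uninformative, and a change of estimand from a mean to a geometric-mean ratio. For log-normal data the two ratios agree only if log-SDs are equal in the arms. For example, log-SD 0.8 on hAF and 1.0 on placebo turns a geometric ratio of 0.50 into an arithmetic ratio of 0.50 × exp((0.64 − 1.00)/2) = 0.42. The sponsor should accept that change knowingly. No new data or patients are needed.

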#### Definition of Adverse Event and Serious Adverse Event

Adverse Event (AE) means any untoward medical occurrence associated with the use of an intervention in humans, whether or not considered intervention-related (21 CFR 312.32 (a)). An event constitutes a disease, a set of related signs or symptoms, or a single sign or symptom.

Serious Adverse Event (SAE): A serious adverse event (SAE) for this population is an adverse event that:

- a) results in death; or
- b) is life-threatening (the patient was, in the view of the site investigator, in immediate danger of death from the event as it occurred); or
- c) requires inpatient hospitalization or prolongs an existing hospitalization; or
- d) results in persistent or significant disability or incapacity; or
- e) results in congenital anomaly/birth defect; or
- f) is any other event that, based upon appropriate medical judgment, may jeopardize the patient's health and may require medical or surgical intervention to prevent one of the other outcomes listed in this definition.

Classification of an Adverse Event (Relatedness, Severity, and Expectedness)

Relatedness: The suspected relationship between study interventions and any adverse event will be determined by the site investigator using the criteria below. Relatedness must be assessed by an investigator and may not be assessed by a research coordinator.

- a) Not Related: The event is clearly related to other factors, such as the subject's clinical state, therapeutic interventions, or concomitant drugs administered to the subject.
- b) Possibly Related: The event follows compatible temporal sequence from the time of beginning the assigned study intervention, but could have been produced by other factors such as the subject's clinical state, therapeutic interventions, or concomitant drugs administered to the subject.
- c) Probably Related: The event follows a reasonable temporal sequence from the time of beginning the assigned study intervention, and *cannot be reasonably explained* by other factors such as the subject's clinical state, therapeutic interventions, or concomitant drugs administered to the subject.

Severity: The severity, which is a measure of intensity, of clinical adverse events and laboratory abnormalities will be recorded by the site investigator and categorized. The following guidelines will be used to describe severity.

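### Related adverse events are to be reported in each arm, but no hAF-minus-saline difference with a confidence interval is specified, so excess risk over saline is never quantified

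*Combined protocol and SAP*

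**What the plan says.** The Synopsis lists the safety of intravenous hAF among the primary objectives. Section 3 makes the safety endpoint a yes/no result for each patient: "Whether the patient experienced any post-randomization, study-related Adverse Events (AEs) while on study (up to 5 days) of treatment".

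Section 8, Statistical Methods, randomizes patients to hAF or saline, 30 per arm. It assesses safety by descriptive reporting of the "incidence proportion of study-related safety adverse events in each study group, with one-sided 95" percent exact binomial intervals. It adds: "No statistical hypothesis test is planned to assess safety, which is consistent even with large Phase III trials". A table then gives lower bounds for the proportion of 30 patients free of a related event (90%, 85%, 80% and 76% for 0, 1, 2 and 3 patients with an event). One conclusion is put into words. If all 30 hAF patients are event-free, "we will be able to state with 95% confidence that the safety of hAF is at least 90" percent.

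Exploratory safety outcomes cover any AE regardless of relatedness, serious AEs and unexpected AEs. No comparative measure is attached to them.

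Earlier in the same section a general rule says "Categorical characteristics will be compared using chi-square test or Fisher exact test", with 95% intervals and p-values for all comparisons. That rule follows a sentence on patient characteristics and on clinical and biomarker outcomes. Adverse events are not mentioned there, and safety then gets its own descriptive paragraph.

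Section 7 has three relatedness categories. An event is possibly related if "The event follows compatible temporal sequence from the time of beginning the assigned study intervention", even where the patient's clinical state could also explain it. The documents do not say which categories make an event study-related for the primary endpoint.

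**The concern.** The saline arm is there to show what happens to similar patients who do not receive hAF. In hospitalized, oxygen-requiring COVID-19 patients dosed daily, some events will be compatible in timing with dosing and also explicable by the illness. If such events count, the hAF bound reflects the illness as well as the product. The quantity that isolates the product is the difference between the arms, and the plan does not name it.

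The two planned intervals do not supply it. Expressed as event-free proportions, each one-sided interval runs from its lower bound up to 100%, so the two always overlap whatever the data. They cannot be combined by eye into a statement about excess risk. A primary objective would then depend on an unplanned calculation by each reader, with the method and the outcomes chosen after the data are known.

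**Working it through.** **Inputs.** 30 patients per arm, one-sided 95% exact intervals and the table of bounds, all from Section 8. The documents give no background rate of related events, no margin and no power for safety. The counts and rates in steps 2 to 4 are therefore assumptions, shown over a range.

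**1. The plan's own table.** With x of 30 patients event-free, the one-sided 95% Clopper-Pearson lower bound is the 5th percentile of a Beta(x, 31 - x) distribution. For x = 30 this is 0.05^(1/30) = 0.905.

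| Event-free | Recomputed | Plan |
|---|---|---|
| 30/30 | 90.5% | 90% |
| 29/30 | 85.1% | 85% |
| 28/30 | 80.5% | 80% |
| 27/30 | 76.1% | 76% |

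The table is right and is one-sided, as stated. (Two-sided bounds would be 88.4, 82.8, 77.9 and 73.5%.)

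**2. What the hAF bound measures if hAF is inert.** Let p be the background proportion of patients with an event counted as related. The chance of the 0/30 needed for the 90% statement is (1 - p)^30.

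| Assumed p | Chance of 0/30 | Mean hAF lower bound |
|---|---|---|
| 5% | 0.95^30 = 21.5% | 83.1% |
| 10% | 0.90^30 = 4.2% | 76.5% |
| 20% | 0.80^30 = 0.12% | 64.6% |

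So the bound falls with the background rate even when the product does nothing.

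**3. The missing estimate.** Take d = p1 - p2 (hAF minus saline), with Wilson 95% limits (l, u) for each arm. The Newcombe limits are:

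- lower: d - sqrt[(p1 - l1)^2 + (u2 - p2)^2]
- upper: d + sqrt[(u1 - p1)^2 + (p2 - l2)^2]

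The Wilson limits are 0.095 to 0.373 for 6/30 and 0 to 0.1135 for 0/30.

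- 6/30 vs 6/30: d = 0, half-width sqrt(0.105^2 + 0.173^2) = 0.202.
- 6/30 vs 0/30: d = 0.200, lower 0.200 - sqrt(0.105^2 + 0.1135^2) = 0.045, upper 0.373.

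| hAF vs saline events | Planned bounds, hAF / saline | Difference (95% CI), points |
|---|---|---|
| 6 vs 6 | 64.3% / 64.3% | 0 (-20.2 to +20.2) |
| 6 vs 0 | 64.3% / 90.5% | +20.0 (+4.5 to +37.3) |
| 9 vs 3 | 53.5% / 76.1% | +20.0 (-0.5 to +39.0) |
| 0 vs 0 | 90.5% / 90.5% | 0 (-11.4 to +11.4) |

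The hAF bound is the same in the first two rows. The planned pair of bounds differs between them, but only the last column gives the size and uncertainty of the excess.

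**4. Would a test help?** Power of Fisher's exact test (two-sided 0.05, 30 per arm) for a true 20-point excess is 44%, 37%, 30% and 26% when the saline rate is 5, 10, 20 and 30%. A test would be underpowered, which supports estimation without one.

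**The case against.** The strongest reply is that the plan already reports both arms on the same measure. A reader might infer that safety is judged from the hAF arm alone and that a harmful product would look the same as an inert one. The documents do not support that. Incidence is reported in each study group, so 6 vs 6 and 6 vs 0 would look different in the planned output, and a crude difference can be taken from the counts. The 90% sentence is a conditional illustration of precision, not a decision rule.

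A reader might also infer that COVID-19 events labelled possibly related will be charged to hAF. That does not follow. The endpoint says study-related without defining it, and the definition of an unanticipated problem in Section 7 lists related and possibly related as separate terms. Section 7 also has a not-related category for events clearly due to other factors, and conditions present at randomization that do not worsen are generally not recorded as adverse events. If possibly related events do count, patients and treating clinicians are blinded, so similar labelling would be expected in both arms. A between-arm comparison would then remain interpretable.

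Nor is the absence of a hypothesis test an error. The exploratory outcomes already include AEs regardless of relatedness and serious AEs, and the DSMB sees treatment assignments. At this sample size the added interval will be wide.

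All of this stands, and it narrows the point without removing it. No difference, ratio or between-arm interval is named for any safety outcome, and the general comparison rule does not clearly reach adverse events. DSMB access to assignments comes with no comparative measure and does not replace the trial's final safety analysis.

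**Conclusion.** The point holds as a gap in the specified analysis. For a primary objective, the plan shows the saline arm but never quantifies the excess risk of hAF over saline or its uncertainty, and its only worded conclusion is an absolute hAF-arm bound. The table arithmetic is correct.

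The size can only be illustrated. An hAF bound of 64% is compatible with no difference (-20 to +20 points) or with an excess of 20 points (+4.5 to +37), depending on the saline count. This rests on 30 evaluable patients per arm and on assumed event counts. How far background illness enters the hAF bound also depends on whether possibly related events count, which the documents leave open. The difference would serve estimation and would not prove safety. Even 0 vs 0 leaves an interval of about 11 points either side.

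**What to change.** In Section 8, keep the per-arm exact intervals and the decision not to test, and make three changes:

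1. Add the hAF-minus-saline difference in the proportion of patients with (a) at least one study-related AE, (b) any AE and (c) any SAE, each with a two-sided 95% confidence interval by a named method such as Newcombe.
2. State whether possibly related events count as study-related for the primary endpoint.
3. Word the 90% statement as the absolute proportion of hAF-arm patients free of a related AE, and report it beside the difference. Say that intervals at 30 per arm will be wide and that the difference is for estimation.

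The cost is a few sentences and one more column in the safety table. No extra data or patients are needed.
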